### **9.3.2      Outcomes**

#### **9.3.2.1      Primary outcomes**

In this study we will use a modified version of an algorithm developed and validated in the [REDACTED] with a sensitivity of 89.8% and a specificity of 79.4% [[R20-3555](#), [R20-3554](#)]. In the original algorithm, only the Logical Observation Identifiers Names and Codes (LOINC) were used for the lipase measurement but since these codes are only available for a subset of patients in Marketscan and Optum databases, to accommodate database needs, the equivalent Current Procedural Terminology (CPT) codes were added to the algorithm. This modified algorithm is:

- The presence of an acute pancreatitis diagnosis from any of the inpatient (not restricted to the primary diagnosis), outpatient, or emergency contacts diagnoses (ICD-9-CM 577.0 or ICD-10-CM K85)  
AND
- A lipase measure within +/- 7 days of the acute pancreatitis diagnosis (using LOINC code of 3040-3 and 2572-6 or CPT code of 83690 for lipase)  
AND
- An abdominal ultrasound (using CPT codes of 76700 and 76705) within +/- 7 days of the acute pancreatitis diagnosis

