- Patients with type 1 diabetes mellitus (T1DM) defined as at least 1 inpatient or outpatient International Classification of Diseases Ninth Revision, Clinical Modification (ICD-9-CM) diagnosis code of 250.x1 or 250.x3 or International Classification of Diseases, Tenth Revision, Clinical Modification (ICD-10-CM) diagnosis code of E10.x in the 6 months prior to the study drug initiation.
- Patients with secondary diabetes or gestational diabetes in the 6 months prior to the study drug initiation.
- Claims for acute or chronic pancreatitis, pancreatic cancer, or other disease of the pancreas any time prior to the study drug initiation.

Treatment line specific inclusion criteria (if feasibility assessment would allow a powered analysis) are:

- For the monotherapy cohort, patients should be new users of empagliflozin or metformin (comparator). To quantify as a new user, no use of either of the two drugs (empagliflozin or metformin) in the previous 6 months is permitted.
- For the dual therapy cohort, patients should be new users of empagliflozin (on a background of metformin) or new users of SU on a background of metformin (comparator). To quantify as a new user, no use of either of the two drugs (empagliflozin or SUs) in the previous 6 months is permitted.
- For the triple therapy cohort, patients should be new users of empagliflozin (on a background of metformin and SU) or new users of TZD on a background of metformin and SU (comparator). To quantify as a new user, no use of either of the 2 drugs (empagliflozin or TZDs) in the previous 6 months is permitted.

All codes used in cohort creation are listed in Appendix 3 and 4.

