### **9.3.1 Exposures**

For this study, eligible patients will be identified from prescriptions/dispensings for the following study medications of interest (index medications):

Study drug will include:

- New therapy with empagliflozin (index medication) for the treatment of T2DM:
  - As monotherapy
  - As dual therapy (on a background of metformin)
  - As triple therapy (on a background of metformin and SU)

Comparator will be:

- New therapy with an oral non-incretin/non-SGLT2i-containing hypoglycaemic agent for the treatment of T2DM:
  - As monotherapy (metformin monotherapy): index medication is metformin
  - As dual therapy (SU on a background of metformin): index medication is SU
  - As triple therapy (TZD on a background of metformin and SU): index medication is TZD

This leads to the following comparisons:

- Monotherapy: Empagliflozin vs metformin
- Dual therapy: Empagliflozin vs SU, both on background of metformin
- Triple therapy: Empagliflozin vs TZD, both on a background of metformin and SU

Fixed-dose combinations will be considered equivalent to their free combination regimens. For instance, initiators of Synjardy will be categorized as dual therapy of empagliflozin. Combinations beyond triple therapy (i.e., use of 4+ glucose lowering drugs) will not be considered.

The index date is defined as the date of the first recorded claim for a qualifying prescription as a new user. Patients are required to have at least 6 months of continuous registration in the database prior to initiation of empagliflozin or a comparator drug (the look-back period). The look-back period was specified to confirm new medication use (i.e., having a first prescription claim for empagliflozin or other oral non-incretin/non-SGLT2i-containing glucose lowering drugs without use in the prior 6 months) and describe baseline parameters, such as prior medical history and medications. The look-back period includes the index date.

The study will be conducted utilizing a modified “as-treated” approach. Study follow-up will start the day after initiation of index medication and will continue until:

- The first occurrence of the outcome

- The date of end of continuous registration in the database
- The date of death
- The date of study end (31 October 2020)

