### **9.7.1 Definitions**

- Index date: Date of the first recorded claim for a qualifying prescription of an index medication as a new user.

- Follow-up: Starts from the day after the index date until the first qualifying event has been met (see [Table 2](#) and [3](#)).
- Look-back period: Patients are required to have at least 6 months of continuous registration in the database prior to initiation of an index medication. The look-back period is defined as 6 months prior to the index date and including the index date. The look-back period was specified to confirm new medication use (i.e. having a first prescription claim for empagliflozin or other oral non- incretin/non-SGLT2i-containing hypoglycaemic without use of these medications in the prior 6 months) and describe baseline parameters, such as prior medical history and medications.
- Grace period: 30 days in main analysis [[c18659315-02](#)] and 90 days [[R18-1760](#), [RRA-21430](#), [P20-07536](#)] in sensitivity analysis.

Table 2 Definitions for study end date

Reason for End of Study or censoring (earliest date of options below)	Definition for End Date
Acute pancreatitis event	Date of the first acute pancreatitis using ICD9 or ICD10 codes
Switch of index medication to another hypoglycaemic agent; see Table 3	Last date of known prescription coverage (date of last prescription fill plus days' supply minus one day) and a grace period equal to 30 days. Exposure time will not extend past the date of the first prescription claim for the newly prescribed agent*
Addition of incretin-based therapy (with continuation of index therapy)	Date of the prescription claim for the added incretin therapy
Addition of SGLT2i (with continuation of index therapy)	Date of the prescription claim for the added SGLT2i therapy
Addition of insulin (with continuation of index therapy)	Date of the prescription claim for the added insulin therapy
Addition of the within treatment line comparator index drug; see Table 3 (with continuation of index therapy)	Date of the prescription claim for the added treatment line comparator index drug
Discontinuation of index drug	Last date of known prescription coverage (date of last prescription fill plus days' supply minus one day) and a grace period equal to 30 days*
End of study data	Date of death#, Date of end of registration, Date of Study End

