6.2.3 Follow up

Follow up starts at the day after the index date until the first qualifying event has been met (see table 2 and 3 of the study protocol).

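### The test windows are not limited to dates after index, the pancreatitis exclusion does not clearly cover the index date, and the start of follow-up is inconsistent, so episodes under way at index can count as on-drug events

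*Protocol*

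**What the plan says.** Protocol 9.3.2.1, like the Variables part of the Abstract, builds a case from three claims: an acute pancreatitis code from any care setting, "A lipase measure within +/- 7 days of the acute pancreatitis diagnosis", and "An abdominal ultrasound (using CPT codes of 76700 and 76705) within +/- 7 days of the acute pancreatitis diagnosis". Neither place says where the tests must lie relative to the index date. Table 2 in 9.7.1 gives the event date as "Date of the first acute pancreatitis using ICD9 or ICD10 codes", so the event is placed by the code and not by the earliest part of the work-up.

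The exclusion in 9.2.2, repeated in the Abstract, is worded "Claims for acute or chronic pancreatitis, pancreatic cancer, or other disease of the pancreas any time prior to the study drug initiation". Section 9.3.1 adds that "The look-back period includes the index date", and protocol 9.7.1 and SAP 6.2.2 agree. The exclusion is not expressed through that look-back: it runs over all earlier history, while the look-back is six months.

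On the start of follow-up the sections differ:

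- **Day after index:** protocol 9.3.1 ("Study follow-up will start the day after initiation of index medication"), protocol 9.7.1 ("Starts from the day after the index date until the first qualifying event has been met") and SAP 6.2.3 ("Follow up starts at the day after the index date until the first qualifying event has been met"). The Abstract and SAP 7.1.1 say the same.
- **Index date:** SAP 7.1.3 runs follow-up from the index date. Protocol 9.7.3 (main analysis) and 9.7.6 item 3 (intention-to-treat) treat patients as exposed from the date of the first prescription claim.

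**The concern.** An incident on-drug event should be an episode that begins after the drug is started. Two routes let in episodes already under way.

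1. **Work-up before index, code after.** A patient has lipase and ultrasound a few days before the first fill, with no pancreatic code, and is first coded a day or two after it. The exclusion looks only for pancreatic disease claims, so it misses this patient, and the outcome definition accepts the earlier tests.
2. **Code on the index date.** Read literally, the exclusion does not remove this patient. With a day-1 start the index-date code is not an event, but a later code for the same episode can then be taken as the first one. Under SAP 7.1.3 the index-date code could itself be the event.

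If such episodes are equally common in both arms, they pull the hazard ratio towards 1. In a study designed to exclude 1.5, that is the favourable direction. If one drug is started more often around an acute illness, the bias could go either way. Protocol 9.8 requires two analysts to reach consistent results independently, and the present wording lets them code day 0 differently. SAP Annex 3 also lists lipase and abdominal ultrasound as covariates, so one early test could serve both as a baseline characteristic and as outcome confirmation.

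**Working it through.** **Date logic.** Let the index date be day 0 and the diagnosis day d. The tests may fall from d − 7 to d + 7.

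- Tests strictly before index require d − 7 ≤ −1, so d ≤ 6. Diagnoses on days 1 to 6 can be confirmed wholly by pre-index tests.
- At d = 7 the earliest permitted test is on day 0.
- From d = 8 the window lies wholly after index.

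The first route is therefore confined to diagnoses in about the first week. The second needs a code on day 0.

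**The plan's sample size.** Inputs from protocol 9.5: rate 0.0022 in both groups, ratio 1.5 under the null, one-sided alpha 0.05, power 80%, 1:1 allocation, one year of follow-up each. The Farrington-Manning restricted estimates under the null are 0.00264 and 0.00176.

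- s0 = √[0.00264 × (1 − 0.00264) + 1.5² × 0.00176 × (1 − 0.00176)] ≈ 0.0812
- s1 = √[0.0022 × 0.9978 × (1 + 1.5²)] ≈ 0.0845
- n = [(1.645 × s0 + 0.842 × s1) / (1.5 × 0.0022 − 0.0022)]² = 34,585.4 per group without intermediate rounding, which matches Table 1

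**Events at stake.**

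- Per arm over one year: 34,585.4 × 0.0022 = 76.1
- In days 1 to 7 at a constant rate: 76.1 × 7 / 365.25 = 1.46 (1.9%); in days 1 to 6: 1.25
- If mean on-treatment follow-up were shorter (assumed), the days 1 to 7 share would be 3.8% at six months and 7.7% at three months
- If that share f were unrelated to drug, a true ratio of 1.5 would read 1.5 × (1 − f) + f = 1.49, 1.48 or 1.46 at one year, six months and three months

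**Episodes already under way at index** would come on top of these. The documents give no count, so k per arm is an assumption. With a true ratio of 1.5 and 76.1 genuine comparator events (114.1 on empagliflozin):

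observed ratio = (114.1 + k) / (76.1 + k)

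The chance of wrongly excluding 1.5 uses a Wald approximation, Φ(−1.645 + ln(1.5 / observed) / SE), with SE = √[1/(114.1 + k) + 1/(76.1 + k)].

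| Assumed k in each arm | Observed ratio | One-sided error at 1.5 (nominal 5%) |
|---|---|---|
| 3 | 1.48 | about 6.0% |
| 5 | 1.47 | about 6.7% |
| 10 | 1.44 | about 8.6% |

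Five in the comparator arm only would give 114.1 / 81.1 = 1.41 and an error of about 11%. Five in the empagliflozin arm only would give 119.1 / 76.1 = 1.57, away from excluding the margin.

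**Planned analyses.** Nothing in 9.7.6 applies a lag or drops early events. Item 1 (primary discharge diagnosis only) drops the test windows, but an admission that straddles the index date can still be counted.

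**The case against.** The case against changing anything is reasonable. Section 9.3.1 labels the registration period before initiation as the look-back and then says it includes the index date, so a programmer could naturally exclude index-date codes. Protocol 9.4 says medical claims carry service dates, so the first route cannot arise from late billing. It needs both tests before index without any pancreatic code, then a new prescription, then a first code within days. Section 9.9.3 notes that the code may be used to rule pancreatitis out, so many work-ups would carry it and trigger the exclusion. The week concerned holds about 2% of expected events, and the 3 to 10 episodes per arm above are assumptions larger than that week's whole expected count. Cutting the window also departs further from the validated algorithm.

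Most of this stands, and it limits the point to a small effect. It does not settle the wording: the exclusion is not tied to the look-back, the tests have no date condition, and the start of follow-up is stated two ways.

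A reader might go further in three directions that the documents do not support:

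- **Index-date pancreatitis is plainly not excluded.** The text is ambiguous, because of the look-back sentence.
- **Every analysis shares the day-1 start, so none could reveal the problem.** The intention-to-treat wording begins on the day the index prescription is filled, and item 1 of 9.7.6 removes the test windows.
- **Such events cannot be caused by the index drug.** Lipase and ultrasound are non-specific, and a test before index does not date the onset of an episode first coded after it.

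**Conclusion.** The point holds as a gap in wording with a small expected effect. Followed literally, the definitions let an episode worked up before index, or coded on the index date, count as an incident on-drug event. On the plan's own figures about 1.5 of 76 events per arm fall in the affected week at a constant rate. The number of episodes carried over is unknown. The 1.48 to 1.44 range rests on assuming 3 to 10 in each arm, and nothing in the documents shows a difference between arms. A reader might infer that the main result would be materially biased or the sample size wrong. Neither follows: the sample size reproduces, and even ten episodes in each arm leave the ratio at 1.44. The change is worth making because equal contamination favours excluding the margin, the listed analyses would not isolate it, and it costs almost nothing to prevent.

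**What to change.** 1. State that the exclusion for pancreatitis and other pancreatic disease applies up to and including the index date.
2. Reconcile protocol 9.7.3, protocol 9.7.6 item 3 and SAP 7.1.3 with protocol 9.3.1, protocol 9.7.1 and SAP 6.2.3, so that follow-up starts the day after index in every analysis.
3. Do not count as incident an episode whose qualifying lipase or ultrasound is dated on or before the index date. Alternatively, leave the algorithm unchanged and add a sensitivity analysis that drops those events, or all events in days 1 to 7.
4. Report the number of events removed in each arm.

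The cost is a few lines of text and one date condition in the outcome program. One or two true early events per arm may be lost, and the case definition becomes slightly stricter in the first week than later. Dropping all of days 1 to 7 lowers the expected rate by 1.9% at one year of follow-up; with 34,585 per arm, the Farrington-Manning power falls from 80.0% to about 79.3%.

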#### **9.3.2.2      Secondary outcomes**

None.

### **9.3.3 Covariates**

Several baseline patient characteristics will be captured in the 6 months prior to the index date. Some of these covariates will be included as covariates in the propensity scores (PS) model.

- Demographics
- Comorbidity indexes: Elixhauser comorbidity index [[R14-4775](#)], Charlson comorbidity index
- Diabetes specific complications
- Comorbidities (e.g. CVD [[R21-0209](#)])
- Prior/concomitant use of other oral glucose lowering drugs
- Prior/concomitant use of other drug(s) associated with acute pancreatitis [[P08-00872](#)]:
  - $\alpha$ -methyldopa, azodisalicylate, bezafibrate, cannabis, carbimazole, codeine, cytosine, arabinoside, dapsone, enalapril, furosemide, isoniazid, mesalamine, metronidazole, pentamidine, pravastatin, procainamide, pyritonol, simvastatin, stibogluconate, sulfamethoxazole, sulinda, tetracycline, valproic acid, all trans-retinoic acid, amiodarone, azathioprine, clomiphene, dexamethasone, ifosfamide, lamivudine, losartan, lynesterol/methoxyethinylestradiol, Mercaptopurine, meglumine, methimazole, nelfinavir, norethindronate/mestranol, omeprazole, premarin, sulfamethazole, trimethoprim-sulfamethazole, acetaminophen, chlorthiazide, clozapine, didanosine, erythromycin, estrogen, L-asparaginase, pegasparagase, propofol, tamoxifen, azathioprine, sulfonamides, tetracyclines, alpha-methyldopa
- Prior/concomitant use of other medications (e.g. cardiovascular medications, full list is added in [annex 5](#))
- Other acute pancreatitis risk factors e.g. abdominal surgery, alcoholism and alcohol abuse, cystic fibrosis, gallstones and other gallbladder and biliary tract disorders, hyperparathyroidism, infection, injury to the abdomen, and lupus
- Specific lab test results (when available, see below and SEAP)
- Coronavirus (COVID-19) infection (this is applicable only to patients who have 2020 data) during the baseline period and follow up

Given the nature of the databases, it will not be possible to include exposure to over-the-counter medications as a covariate in the analysis.

The list of covariates is provided in Appendix 5 and all practical definitions and codes can be found in the statistical epidemiological analysis plan (SEAP).

Laboratory test results in a subset of patients:

For a subset of about 40-50% of patients in Optum Clininformatics and 5-15% in MarketScan, laboratory test results are available through linkage with two nationally operating lab test provider chains. Available laboratory test results during the 6 months prior to the index date will be identified using LOINC codes. After PS matching, if major imbalance is observed, patient characteristics with and without lab test results might be further explored as optional additional analysis.

In case of multiple values available for a specific lab result, we will only consider the closest to the date of drug initiation. Laboratory tests of interests are provided in [Annex 5](#) and include amylase (U/L); lipase (U/L); white cell count (G/L); red cell count (T/L); haemoglobin (g/L); haematocrit (%); thrombocyte (G/L); C-reactive protein (mg/L); creatinine ( $\mu$ mol/L); urea (mmol/L); serum bilirubin ( $\mu$ mol/L); GGT (mmol/L); GOT (mmol/L); GPT (mmol/L); ALP (mmol/L); uric acid (mmol/L); cholesterol (HDL, LDL) (mmol/L); triglycerides (mmol/L); serum protein (g/L); albumin (g/L); C-peptide (pmol/L); HgbA1C (%); OGTT test glucose (mmol/L) and insulin level (pmol/L) at 0, 60 and 120 min [\[R20-3572\]](#).

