In the past ten years, numerous studies assessed the association between pancreatitis and hypoglycemic agents in the US [[R18-1760](#), [P19-09574](#), [R13-3873](#), [R11-0776](#), [R19-3424](#), [P13-04390](#), [P13-16900](#), [R20-0777](#)], Canada [[P19-09574](#)], UK [[P17-03843](#), [P14-06737](#)], Denmark [[P15-05208](#)], and in Asia [[R19-3425](#), [R19-3426](#), [R19-3427](#), [R19-3428](#), [R19-3429](#), [R11-5180](#), [P16-11950](#), [R19-3430](#)]. Certain diabetes drug classes, for instance incretin-containing medications (including dipeptidyl peptidase 4 inhibitors (DPP-4i; such as sitagliptin, saxagliptin, linagliptin, alogliptin) and glucagon-like peptide-1 receptor agonists (GLP-1 RA; such as exenatide, liraglutide, lixisenatide, dulaglutide, semaglutide) [[P13-15588](#)]), have been associated with the risk of developing acute pancreatitis. Results vary from protective to null associations to 2-3 fold elevated risk of acute pancreatitis depending on the design, population, treatments and comparators studied [[R18-1760](#), [P19-09574](#), [R13-3873](#), [R11-0776](#), [R19-3424](#), [P13-04390](#), [P13-16900](#), [R20-0777](#), [P19-09574](#), [P17-03843](#), [P14-06737](#), [P15-05208](#), [R19-3425](#), [R19-3426](#), [R19-3427](#), [R19-3428](#), [R19-3429](#), [R11-5180](#), [P16-11950](#), [R19-3430](#)]. Recently an observational study was conducted using large claims databases in the US (Truven Marketscan Commercial Claims and Encounters (CCAE) and Medicare Supplemental (MDCR) Database, and Optum Extended Socio-Economic (SES)) to assess the risk of acute pancreatitis in T2DM patients newly exposed to canagliflozin compared to other oral hypoglycemic agents. Six different cohorts of new users of DPP-4is, GLP-1 RAs, sulfonylureas (SUs), thiazolidinediones (TZD), insulin, and other antihyperglycemic agents (AHA) were identified and compared separately with the new users of canagliflozin. Overall, no consistent difference in the risk of acute pancreatitis was observed when comparing canagliflozin with other oral glucose lowering drugs, not with regards to databases, nor with regards to different comparator groups [[RRA-21430](#)]. This inconsistent observation could have several reasons: 1) cohorts were not properly matched concerning previous use of AHA 2) cohorts were not matched with regards to acute pancreatitis risk factors e.g. gall stones 3) concomitant AHA treatment were allowed without restriction. Moreover, because of the heterogenous comparator and residual confounding, no conclusion could be made based on the study results.

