## **9.5 STUDY SIZE**

All patients with T2DM who newly initiate therapy with empagliflozin or study comparator who meet the inclusion and exclusion criteria will be included in the analysis.

Event rate of acute pancreatitis reported in patients with T2DM who are treated with canagliflozin was reported to be 2.2 per 1000 PY [\[RRA-21430\]](#). This rate was used for sample size calculation using the formula of Farrington and Manning (maximum likelihood method) [\[R14-3295\]](#).

Null hypothesis H0:  $\pi_2 / \pi_1 \geq 1.5$  (non-inferiority)

A single stage (fixed sample size) design was chosen.

For specified  $\alpha = 0.05$  and rates  $\pi_1 = 0.0022$  and  $\pi_2 = 0.0022$  (odds ratio of 1.000) the power (1 -  $\beta$ ) is 80.0% if the test stages consist of the sample sizes given in the last two columns of [Table 1](#).

The computation assumes an allocation ratio (n2/n1) = 1 (Table 1). It is assumed that all patients have 1 year of follow up.

**Table 1** Number of empagliflozin initiators and empagliflozin-exposed person-years needed to detect a HR of 1.5 and 2.0 with a power of 80% and  $\alpha = 0.05$  under 1:1 matching ratio

Hazard ratio (HR)	Information rate	Bunds accept $H_0$	Bunds reject $H_0$	sign.level one-sided	$\alpha$ spent	$\beta$ spent	power achieved	Observations per exposure group	Overall observations
1.5	1.0	1.645	1.645	0.0500	0.0500	-	0.8000	34585.4	69170.8

ADDPLAN Adaptive Design Software 2019 and SAS 9.4 software ( ) were used to calculate the sample size.

Analysis of this study will be initiated as soon as a sufficient sample size to exclude a HR of 1.5 with 80% power is reached. Based on a feasibility assessment conducted in Optum and MarketScan databases using data between 1 August 2014 and the latest data-cut available in MarketScan (30 September 2020) and Optum (31 March 2021), the dual-therapy cohort was reported with the highest number of empagliflozin initiators, therefore meta-analysis of the dual therapy cohorts including the data from the MarketScan and Optum databases will be the main analysis of this study as it will be the only powered analysis.

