### **9.9.1 Data source**

The source claims data include limitations with respect to certainty of the capture of exposure, covariates, and outcomes. As a comprehensive insurance database, essentially all billable medical services will result in claims for reimbursement, so that the certainty of capture is tied to likelihood of a claim being submitted to the insurer.

Although duration of diabetes may represent a risk factor for the study outcome, this covariate will be incompletely captured since the patient history in the dataset is relatively short (at least 12 months, and an average of approximately 2 years), and a first claim within the database may not represent diabetes onset since the condition can be latent for some time and is typically not treated with hypoglycaemic medications at its diagnosis.

New initiators are operationally defined as patients with no use in the prior 6 months. This does not ensure, however, that patients have never used the drug of interest; the possibility remains that these patients were treated at some prior time point before they enrolled in their insurance plan.

There is potential for misclassification of dose based on healthcare utilization data, but the “days supply” field is expected to be fairly accurate. Similar concern may be present for exposure classification as well, but we expect the drug codes utilized in the data sources will appropriately represent the drug that is being classified.

Medication use in administrative healthcare databases is restricted to prescription drug medication. Consequently, the use of over-the counter (OTC) medications (e.g., OTC aspirin) is not captured. Additionally, the indication of a claim for prescription medications does not confirm whether the medication was actually taken by the patient or taken as prescribed.

It is estimated that two databases (MarketScan and Optum CDM) have about 10-15% overlap and it is not possible to identify duplicates and remove them between the two databases because patients are de-identified. It is not expected that this overlap impacts the results of this study because it will be much smaller in the study population. Furthermore, there is a sensitivity analysis to consider several scenarios of overlap in patients between the MarketScan and Optum (e.g., 0%, 10%, 20%, etc.), and 95% CIs of primary outcome will be adjusted accordingly.

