Study participants in the empagliflozin group will be 1:1 matched with comparators to account for confounders. After PS matching, study participants will be matched based on the calendar quarter year of the cohort entry to help minimize residual confounding.

Although we will try to measure and include all available confounders in the PS models, some important variables e.g. alcohol abuse or smoking which are correlated with the outcome are not available for all study participants. Furthermore, study participants in the comparator groups are probably more prone to have lower socioeconomic status which is a potential for channelling bias that is not easy to detect in our study. These patients may also have different background risk for alcohol use and smoking.

Some of the outcome risk factors, e.g. infection, are only captured via hospital admission claims. Therefore, infections not resulting in hospitalization cannot be captured in this study and this increases the risk of residual confounding.

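### Chronic pancreatitis risk factors are read from 6 months of claims and infection from hospital claims only, although the plan uses longer look-backs and outpatient codes elsewhere; part of the residual confounding is avoidable

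*Protocol*

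**What the plan says.** Protocol 9.3.3 sets the window: "Several baseline patient characteristics will be captured in the 6 months prior to the index date". SAP 6.2.2 repeats the 6-month look-back, index date included. Alcohol abuse and gallstones with other biliary disease are listed in 9.3.3. SAP Annex 3 adds hypertriglyceridemia (category 9) and smoking (category 1). Neither document gives these a longer window. Under Protocol 9.7.7 and SAP 9.2, a condition without a code counts as not present.

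On infection, Protocol 9.9.2 says that "infections not resulting in hospitalization cannot be captured in this study" and accepts that this raises residual confounding.

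Other parts of the plan reach further:

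- The exclusion in 9.2.2 covers "Claims for acute or chronic pancreatitis, pancreatic cancer, or other disease of the pancreas any time prior to the study drug initiation".
- The eCVD subgroup in 9.7.6 uses 12 months of history.
- T2DM (9.2.2) and the outcome (9.3.2.1) both accept outpatient codes.
- Section 9.9.1 says that "essentially all billable medical services will result in claims for reimbursement".
- Section 9.9.1 also says that "the patient history in the dataset is relatively short (at least 12 months, and an average of approximately 2 years"), whereas eligibility in 9.2.2 asks for only 6 months.

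None of the seven sensitivity analyses in 9.7.6 lengthens the covariate window or widens the setting for infection.

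**The concern.** Protocol section 7 names gallstones, alcohol and hypertriglyceridemia as the commonest causes of pancreatitis. These are long-standing conditions that may be coded only now and then. A patient whose gallstones or alcohol abuse were last coded 9 months before index enters the propensity score model as unaffected and can be matched to someone who truly is. The balance table cannot show this, because it is built from the same 6-month variables.

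Section 7 also criticises the earlier canagliflozin study because "cohorts were not matched with regards to acute pancreatitis risk factors e.g. gall stones". Good capture of those factors is therefore part of this study's rationale. At stake is an unmeasured imbalance that shifts the hazard ratio in a study meant to exclude 1.5. A downward shift would make exclusion too easy; an upward shift would cost power.

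For infection, the documents give no reason why outpatient codes serve for T2DM and pancreatitis but not for this covariate.

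**Working it through.** **Step 1. The plan's own figure.** Protocol 9.5 takes an event rate that "was reported to be 2.2 per 1000 PY" in both groups, one-sided α = 0.05, 80% power, 1:1 allocation, one year per patient and a null ratio of 1.5. On method: "This rate was used for sample size calculation using the formula of Farrington and Manning (maximum likelihood method").

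- n per group = [(z₀.₉₅√V₀ + z₀.₈₀√V₁) / (π₂ − 1.5π₁)]²
- V₁ = 1.5²·π₁(1−π₁) + π₂(1−π₂) = 0.007134
- V₀ is the same expression at the rates constrained to a ratio of 1.5 (0.001760 and 0.002640), giving 0.006585
- Result: 34,585.4 per group, which matches the protocol exactly.

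Expected events are 2 × 34,585.4 × 0.0022 ≈ 152, so SE(log HR) ≈ √(4/152) ≈ 0.16. The covariate window does not enter this calculation.

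**Step 2. Residual bias from one binary risk factor.** The documents give no prevalence, rate ratio or capture rate, so all of these are assumptions: true prevalence 8% in one arm and 5% in the other, rate ratio (RR) 3 or 5, and capture s of 40% in 6 months or 75% over all available history. Matching is assumed to balance the recorded indicator perfectly.

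True prevalence among patients recorded as unaffected is p(1−s)/(1−ps):

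- s = 0.40: 0.048/0.968 = 0.0496 and 0.030/0.980 = 0.0306
- s = 0.75: 0.020/0.940 = 0.0213 and 0.0125/0.9625 = 0.0130

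The bias factor is [1 + (RR−1)p₁] / [1 + (RR−1)p₀], where p₁ and p₀ are these residual prevalences in the higher- and lower-prevalence arms:

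| RR | 6 months (s = 0.40) | All history (s = 0.75) |
|---|---|---|
| 3 | 1.036 | 1.016 |
| 5 | 1.068 | 1.032 |

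If the SU arm has the higher prevalence, the reciprocals apply. The factor describes recorded-negative patients. Adding the recorded positives (about 2.6%, the mean of 0.40 × 8% and 0.40 × 5%) takes 1.036 to about 1.033.

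**Step 3. Effect on the conclusion.** With bias factor b and 152 events, the chance of excluding 1.5 when it is true is Φ[√(152/4)·(ln 1.5 − ln(1.5b)) − 1.645].

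- Step 2 inputs, higher prevalence in the SU arm: 7.7% falls to 6.1% with the longer look-back (RR 3), and 10.7% to 7.3% (RR 5), against a nominal 5%.
- A wider imbalance (5% empagliflozin, 10% SU; capture 50% rising to 70%): 9.1% falls to 7.4% (RR 3), and 14.3% to 10.2% (RR 5).
- The reverse imbalance (6% empagliflozin, 4% SU; RR 3; capture 50% rising to 70%): the error is then conservative, and power at a true HR of 1.0 moves from 76.8% to 78.2%.

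**Step 4. Infection.** No calculation is possible. The hospital-only limit in 9.9.2 sits beside the all-services statement in 9.9.1 and the use of outpatient codes for T2DM and the outcome, and no explanation is given.

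**The case against.** The case for leaving the plan as it is has substance.

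- A fixed window gives every patient the same time in which to be recorded. An all-history window makes capture depend on length of enrolment.
- Only 6 months is guaranteed. The 2-year figure in 9.9.1 is an average and is not said to be all pre-index.
- Section 9.9.3 says that alcohol use, obesity and some biliary disease are under-reported in claims, which a longer window cannot fully cure.
- SAP Annex 3 holds partial proxies: skin infections, systemic antibacterials, hyperlipidaemia and lipid-modifying agents. The single-factor calculation ignores them.
- The gain is small against sampling error: moving from 1.036 to 1.016 is about 0.02 on the log scale, or 0.12 SE.
- The infection limit is disclosed.
- Sensitivity analysis 2 in 9.7.6 excludes cases coded as biliary or alcohol-induced.

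Most of this stands and limits the benefit. The last two points do not answer the concern. Disclosing a limit does not explain it when outpatient claims are in use elsewhere. Dropping cases by coded cause does not improve the matching of patients.

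A reader might also infer that the study repeats the canagliflozin study's weakness. It does not: that study is faulted for not matching on such factors, and this plan captures them as covariates, with limited look-back. Nor do the documents show that the HR will be pushed down. Section 9.9.2 says only that alcohol and smoking risk may differ between groups, and gives no direction for gallstones or triglycerides. Several factors could add up or cancel.

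**Conclusion.** The concern holds as an avoidable part of the residual confounding. The 6-month window, the hospital-only capture of infection, and the use of longer look-backs and outpatient codes elsewhere are all in the text. That earlier claims exist for many patients follows from 9.9.1 and from the any-time exclusion; it does not mean that two years are available for everyone.

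Size and direction rest wholly on assumptions. With rate ratios of 3 to 5 and the prevalences and capture rates above, one factor contributes roughly 1.04 to 1.07, or its reciprocal, and a longer look-back about halves that. The effect is on bias, not on sample size. It is modest beside an SE of 0.16, but additional patients would not remove it. This is a worthwhile, low-cost improvement, not a flaw that invalidates the design.

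**What to change.** - Keep the 6-month entry rule, and keep the 6-month window for acute conditions and medications.
- In Protocol 9.3.3 and SAP Annex 3 (category 9, plus alcohol and smoking in category 1), add for each chronic risk factor an indicator for any record on or before index, from any encounter type, over all available registration.
- Add length of prior registration as a covariate and show it in the balance table.
- Use these variables in the propensity score model or, at minimum, in a sensitivity analysis pre-specified in 9.7.6.
- Define infection from any encounter type within the 6-month window.
- Reconcile the 12-month minimum history in 9.9.1 with the 6-month eligibility rule in 9.2.2.

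The cost is a change of covariate definitions and some programming, with the same claims and code lists. The eligible cohort and the 34,585 per group are unaffected. The downside is that look-back length will differ between patients; including registration length handles this only in part, which is a fair reason to prefer the sensitivity-analysis route if its balance between groups is poor.
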